3.8.5 Clinical Laboratory Evaluation

Hematology, serum chemistry, lipid profile (HDL, LDL, cholesterol, and triglycerides), and urinalysis parameters will be collected in this study. The hematology, serum chemistry, and lipid profile parameters as well as their changes from baseline will be summarized with descriptive statistics by visit. The shift from baseline in hematology, serum chemistry, lipid profile, and urinalysis parameters will be summarized by visit.

Treatment-emergent laboratory/vital signs changes (TELVC) will be defined for post-baseline values according to the reference ranges given in **Appendix E**. Number of subjects with TELVC will be summarized by visit.

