An AE includes but is not limited to any clinically significant worsening of a subject's pre-existing condition. An abnormal laboratory finding (including ECG finding) that requires an action or intervention by the investigator, or a finding judged by the investigator to represent a change beyond the range of normal physiologic fluctuation, should be reported as an AE. The worsening and/or flare of SLE disease activity will be captured in the disease activity assessments or other study-specific CRFs (ie, SLE Increase in Disease Activity CRF), and not recorded as an AE, unless it meets the definition for an SAE or AESI. If clinical sequelae are associated with a laboratory abnormality, the diagnosis or medical condition should be reported (eg, renal failure, hematuria) not the laboratory abnormality (eg, elevated creatinine, urine RBC increased). Abnormal laboratory values that are not, in the investigator's opinion, medically significant and do not require intervention should not be reported as AEs.

Adverse events may be treatment emergent (ie, occurring after initial receipt of investigational product) or nontreatment emergent. A nontreatment-emergent AE is any new sign or symptom, disease, or other untoward medical event that begins after written informed consent has been obtained but before the subject has received investigational product.

Elective treatment or surgery or preplanned treatment or surgery (that was scheduled prior to the subject being enrolled into the study) for a documented pre-existing condition that did not worsen from baseline is not considered an AE (serious or nonserious). An untoward medical event occurring during the prescheduled elective procedure or routinely scheduled treatment should be recorded as an AE or SAE.

Nonserious AEs will only be captured during the first year of subject's participation in the study; however, nonserious AEs that result in interruption of investigational product and/or discontinuation from the study will be captured at any time during the subject's participation in the study. Serious adverse events and AESIs will be captured throughout the entire study participation.

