7.3 Endpoints

7.3.1 Primary Endpoint

The primary objective of this study is to evaluate the long-term safety and tolerability of IV MEDI-546 in adult subjects with moderately-to-severely active SLE. The safety and tolerability of MEDI-546 will be assessed primarily by summarizing treatment-emergent AEs (TEAEs) and treatment-emergent SAEs (TESAEs). Other variables used for the safety assessments will include serum chemistry, hematology, urinalysis, vital signs, physical examination, ECG, and concomitant medications.

All TEAEs and TESAEs will be summarized by system organ class and preferred terms, by severity and relationship to investigational product. No formal statistical testing will be performed. Other safety variables as well as their changes from baseline (if applicable) will be summarized descriptively.

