Appendix 8 Guidance for Abnormal Liver Function Tests Management

This guidance is based on the July 2009 Guidance for Industry Drug-Induced Liver Injury: Premarketing Clinical Evaluation.

Section IV of the US FDA document deals with the clinical evaluation of and monitoring of drug-induced liver injury, and this protocol-specific guidance has adopted the recommendations on detection of drug-induced liver disease, confirmation of abnormal ALT/AST with regard to retesting, follow-up observation, advice on appropriate history gathering and advice on the need for obtaining additional laboratory tests and consultations as needed. MedImmune has adopted a conservative approach to holding administration of investigational product based on abnormal liver function tests (LFTs) until a full understanding of the event has been understood by the principle investigator and the medical monitor. This understanding is required so that the principle investigator, in consultation with the medical monitor, can reach a decision as to whether dosing can be continued or whether it is advisable to stop investigational product permanently. The US FDA document acknowledges there is no published consensus on how this decision should be made but this protocol-specific guidance requires involvement of the medical monitor at any early stage of clinically significant increases in ALT/AST to provide additional information on accumulating clinical experience of MEDI-546 as well as input from the investigator regarding the nature of the subject and other factors that may be relevant. This approach will provide the balance necessary to permit learning about the investigational product while maximizing safety concerns to minimize the potential for functional liver impairment and damage. There are 2 separate parts to the guidance to detect clinically significant liver injury depending on whether the subject entered the study with normal or mildly elevated (up to $2 \times ULN$) ALT/AST or on more severe abnormalities in subjects with $ALT/AST > 2 \times ULN$ at baseline.

For the purpose of this document, LFTs will be AST, ALT, total bilirubin, and alkaline phosphatase.

The decision to include subjects in this clinical trial with baseline LFT abnormalities is supported by the US FDA guidance.

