3 STATISTICAL METHODS

3.1 General Considerations

Categorical data will be summarized by the number and percentage of subjects in each category. Continuous variables will be summarized by descriptive statistics, including mean, standard deviation, median, minimum, and maximum. Data will be provided in data listings sorted by treatment group and subject identification (SID) number.

Baseline will be defined as the last non-missing observation on or before Day 1 prior to investigational product administration of study CD1145.

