3.8.6 Other Safety Evaluations

3.8.6.1 Vital Signs

Vital sign results, as well as changes from baseline, will be summarized with descriptive statistics by visit. Treatment-emergent laboratory/vital signs changes (TELVC) will be defined for post-baseline values according to the reference ranges given in **Appendix F**. Number of subjects with TELVC will be summarized by visit.

For dosing visits, only measurements prior to dosing will be considered for by-visit presentations. In the case of multiple measurements prior to dosing, the first measurement will be used for by-visit presentations, but all measurements will be considered for the TELVC classification.

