6 APPENDIX

Appendix E

REFERENCE RANGES AND TELVC FOR LABORATORY VALUES

Parameter	Unit	Low value	Low decrease	High value	High increase
Haematology					
Haemoglobin	g/L	≤6	NA	≥20	NA
		≤7 and decrease from BL ≥1.5			
Haematocrit	V/V	≤0.18	NA	≥0.64	NA
		≤0.21 and decrease from BL ≥15%			
WBC	10E9/L	≤2, <1	NA	≥20	NA
Neutrophils	10E9/L	<0.5	NA	≥20	NA
		<1.0 and decrease from BL ≥0.5			
Lymphocyte	10E9/L	≤0.5, ≤0.25	NA	≥10.0	NA
Monocytes	10E9/L	NA	NA	≥1.4, ≥5.0	NA
Eosinophils	10E9/L	NA	NA	≥1.5, ≥5.0	NA
Basophils	10E9/L	NA	NA	≥1.0, ≥2.0	NA
Platelet Count	10E9/L	≤20		≥600	NA
		≤50 and decrease from BL ≥25			
INR		NA	NA	≥4.5	NA
Biochemistry					
ALT	IU/L	NA	NA	≥3 x ULN, ≥5 x ULN	NA
AST	IU/L	NA	NA	≥3 x ULN, ≥5 x ULN	NA
ALP	IU/L	NA	NA	≥3 x ULN	NA
CK	IU/L	NA	NA	≥500, ≥2000	NA
GGT	IU/L	NA	NA	≥5 x ULN	NA
Total Bilirubin	μmol/L	NA	NA	≥2 x ULN	NA

Parameter	Unit	Low value	Low decrease	High value	High increase
Albumin	g/L	≤ 20	NA	≥ 100	NA
		≤ 25 and decrease from BL	≥ 10	≥ 70 and increase from BL	≥ 10
BUN	mmol/L	NA	NA	≥ 18	NA
Creatinine	umol/L	NA	NA	$\geq 140, \geq 190$	NA
Sodium	mmol/L	≤ 132	NA	≥ 152	NA
Potassium	mmol/L	≤ 3	NA	≥ 5.5	NA
Chloride	mmol/L	≤ 90	NA	≥ 120	NA
Fasting Glucose	mmol/L	≤ 2.5	NA	$\geq 7.0, \geq 11.1$	NA
Total Cholesterol	mmol/L	NA	NA	≥ 7.25	NA
Urinalysis					
Urine protein/ creatinine ratio	g/mmol	NA	NA	≥ 0.395	NA
Fasting lipid profile					
HDL	mmol/L	≤ 0.8	NA	NA	NA
LDL	mmol/L	NA	NA	≥ 5.2	NA
Triglycerides	mmol/L	NA	NA	$\geq 3.6, \geq 5.4$	NA

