Appendix F

REFERENCE RANGES AND TELVC FOR VITAL SIGNS

Parameter	Unit	Low value	Low decrease	High value	High increase
Pulse	Beats per minute	≤ 50 ≤ 50 and decrease from BL ≥ 20	NA	≥ 120 ≥ 120 and increase from BL ≥ 20	NA
Systolic blood pressure	mmHg	≤ 90 ≤ 90 and decrease from BL ≥ 20	NA	≥ 160 ≥ 160 and increase from BL ≥ 20	NA
Diastolic blood pressure	mmHg	≤ 50 ≤ 50 and decrease from BL ≥ 10	NA	≥ 100 ≥ 100 and increase from BL ≥ 10	NA

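### Apart from six change-from-baseline tiers, the laboratory TELVC limits carry no baseline condition, so an unchanged abnormality counts as treatment-emergent; the absolute vital-sign limits share the gap

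*SAP*

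**What the plan says.** SAP 3.8.5 defines the laboratory flag in one sentence: "TELVC) will be defined for post-baseline values according to the reference ranges given in" Appendix E. It then asks for the number of subjects flagged at each visit. The section does not require that the limit was unmet at baseline or that the value has worsened.

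Appendix E lists mostly absolute limits; the ALT and AST entries, for example, are "≥3 x ULN, ≥5 x ULN". Haemoglobin, haematocrit, neutrophils and platelets (low side) and albumin (both sides) add a milder limit that counts only with a stated change from baseline.

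Appendix F gives every vital-sign limit twice, once alone and once with a change. For low pulse the second form is "≤ 50 and decrease from BL ≥ 20", and the same threshold of 50 also stands by itself. SAP 3.8.6.1 adds that "all measurements will be considered for the TELVC classification". Section 3.8.5 has no matching sentence.

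SAP 3.1 supplies a baseline that could be used: "Baseline will be defined as the last non-missing observation on or before Day 1 prior to investigational product administration". Protocol 7.3.1 places laboratory data in a supporting role: "Other variables used for the safety assessments will include serum chemistry, hematology, urinalysis".

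**The concern.** TELVC stands for treatment-emergent laboratory/vital signs changes, and a value that has not moved since before the first dose is not a change. The protocol shows how it uses the term in 6.1.1: "Adverse events may be treatment emergent (ie, occurring after initial receipt of investigational product) or nontreatment emergent". That sentence concerns adverse events, but it indicates how a reader will take the table title.

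The protocol foresees abnormal baselines. Its Appendix 8 refers to "The decision to include subjects in this clinical trial with baseline LFT abnormalities" and splits the liver guidance by baseline ALT/AST.

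The study is open-label with no control arm, so a reader cannot subtract a background level from a count that mixes old and new abnormality. The old part could be lupus itself or earlier anifrolumab, since two of the three 1:1:1 arms of Study CD-IA-MEDI-546-1013 were active.

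**Working it through.** The plan states no figure for this point, so there is none to reproduce. The check is a count of the limits and a test of the rules as written.

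**1. Parameters in Appendix E.** 10 haematology + 14 biochemistry + 1 urine + 3 lipid = 28. Five have a change-from-baseline tier, so 28 − 5 = 23 are absolute only (11 with two tiers, 12 with one). All 28 have at least one stand-alone absolute limit.

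**2. Limits by parameter and direction.** 16 + 19 + 1 + 3 = 39. Those with a change tier are haemoglobin low, haematocrit low, neutrophils low, platelets low, albumin low and albumin high, which makes 6. Without one: 39 − 6 = 33.

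**3. Appendix F.** 3 parameters × 2 directions = 6 limits. Each has a change tier, but at the same threshold as its stand-alone limit. The change tier therefore marks a subset and adds no subject to a count of any TELVC. An unchanged vital sign beyond the limit is flagged just as a laboratory value is.

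**4. Rules applied to assumed values (10⁹/L).**

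| Parameter | Baseline | Post-baseline | Flagged as written? | Why |
|---|---|---|---|---|
| Lymphocytes | 0.45 | 0.45 | Yes | ≤0.5 is absolute |
| Neutrophils | 0.45 | 0.48 | Yes, though improved | <0.5 is absolute |
| Platelets | 18 | 18 | Yes | ≤20 is absolute |
| Neutrophils | 0.8 | 0.8 | No | <1.0 needs a fall of ≥0.5 |
| Platelets | 45 | 45 | No | ≤50 needs a fall of ≥25 |

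If the rule also requires the limit to be unmet at baseline, the first three are no longer flagged.

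**5. Which absolute-only parameters have a fitting Day 1 value.** From the 23, take out:
- INR, which is not routinely tested (protocol Appendix 8)
- total cholesterol, HDL, LDL and triglycerides, first drawn at Week 4 (Table 5.1-1)
- glucose, which Appendix E specifies as fasting, while protocol 5.2.5 requires fasting only for the lipid profile

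23 − 1 − 4 − 1 = 17.

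**6. How often one subject can appear** (Tables 5.1-1 and 5.1-2).
- Routine chemistry and haematology: Weeks 4 and 8, 12 twelve-weekly visits, Week 156, Visits 41 and 43 = 2 + 12 + 1 + 2 = 17
- Urine protein/creatinine: 12 + 1 + 2 = 15
- Lipids: Weeks 4, 48, 96, 144 and Visit 43 = 5, and only if an earlier value serves as baseline
- Glucose: fasting is required only at those same five visits

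With 240 subjects in a visit row, each affected subject adds 1/240 = 0.42 percentage points, and more as subjects leave. The SAP plans no total across visits.

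**7. Repeat results.** Without a sentence in 3.8.5, the SAP 3.1.1 default applies: one value per window, the nearest to the target day, with ties going to the earlier. Protocol 5.2.5 asks for abnormal results to be repeated, ideally at 24 to 48 hours. Assume that interval runs from the draw. A repeat r days after a draw at offset d from target then replaces it when |d + r| < |d|:
- r = 1 needs d ≤ −1
- r = 2 needs d ≤ −2
- a draw on or after the target day is never replaced

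Example with assumed values: Week 12 has target Day 7 × 12 + 1 = 85. Lymphocytes are 0.4 on Day 82 and 0.6 on repeat at Day 84. Day 84 is used and the abnormal value leaves the count.

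**The case against.** Several points weigh on the other side.

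- **Appendix E does use baseline.** A reader might infer that laboratory TELVC has no baseline condition at all. The documents do not support that: six tiers require a change. The point holds for the absolute limits only.
- **The contrast with vital signs.** A reader might also infer that vital signs are handled correctly. They are not; the stand-alone limits in Appendix F carry the same flaw.
- **The limits may be deliberate.** TELVC is a SAP term defined by its own tables, and a change tier was added where one was wanted. This is a fair reading. But an absolute screen counts values beyond a limit, which is not what the name says.
- **Other outputs cover it.** SAP 3.8.5 also plans shifts from baseline by visit, and changes from baseline for all but urinalysis. These do help to separate old from new abnormality. Their categories are not tied to the Appendix E limits, so they cannot be used to correct the TELVC counts.
- **The repeat issue is narrow.** The all-measurements sentence in 3.8.6.1 sits in a rule for dosing visits, where vital signs are taken several times; laboratory samples are usually a single draw. A count is lost only when the draw was early, the repeat is nearer the target day and the value is back inside the limit. The windows are left to the statistical programming plan, which is not available. This part is secondary.

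**Conclusion.** The point holds as a minor one. Followed as written, the rule labels unchanged, and even slightly improved, values beyond an absolute limit as treatment-emergent. That can happen for 33 of 39 laboratory limits with no change tier to separate new from old, and for the absolute part of the other six. The six vital-sign limits share the problem.

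A stronger reading would be that the TELVC tables are materially inflated. The documents do not support it. They do not say how many subjects are beyond a limit at baseline, and the Study CD-IA-MEDI-546-1013 entry limits are not given. The number may be zero. The repeat-value effect runs the other way, and its frequency cannot be derived either, so the net direction is unknown.

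The conclusion rests on the SAP text. It assumes that the programming plan does not already add a baseline condition.

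**What to change.** In SAP 3.8.5, and likewise for the absolute limits in 3.8.6.1 and Appendix F:

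1. Count a TELVC only when the limit is met post-baseline and was not met at baseline, or when the value moves to a worse tier. Keep the change-from-baseline tiers as written.
2. Show subjects already beyond the limit at baseline in a separate row with their worst post-baseline value, so that worsening in the 12 single-tier parameters is not hidden.
3. Show subjects with no baseline value in their own row. State whether a Study CD-IA-MEDI-546-1013 value may serve as baseline for lipids, and which value serves for fasting glucose.
4. As a secondary step, add an any-time post-baseline laboratory count from all scheduled, repeat and unscheduled results. Leave the by-visit counts on windowed values.

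The cost is wording in the SAP and programming plan, a baseline flag, and extra rows. For the laboratory tables, three rows per limit gives 39 × 3 = 117. If every tier is shown separately there are 39 + 11 second absolute tiers + 6 change tiers = 56 thresholds, or 56 × 3 = 168 rows. Vital signs need two rows per limit, 6 × 2 = 12. No new data are needed.

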5.2.5 Clinical Laboratory Tests

Clinical laboratory safety tests will be performed in a central clinical laboratory. Urine pregnancy tests may be performed at the site using a licensed test (dipstick). Abnormal laboratory results should be repeated as soon as possible (preferably within 24 to 48 hours).

Subjects will be required to fast for at least 8 hours prior to the assessment of lipid profile (high-density lipoprotein [HDL], low-density lipoprotein [LDL], cholesterol, and triglycerides) according to the Schedule of Study Procedures (Table 5.1-1 and Table 5.1-2).

The following clinical laboratory tests will be performed (see Table 5.1-1 and Table 5.1-2 for the schedule of tests):

Serum Chemistry

- Calcium
- Chloride
- Potassium
- Sodium
- Aspartate transaminase (AST)
- Alanine transaminase (ALT)
- Alkaline phosphatase (ALP)

- Gamma glutamyl transferase (GGT)
- Blood urea nitrogen (BUN)
- Creatinine
- Total bilirubin (reflexively fractionated if elevated)
- Glucose
- Albumin
- Creatine kinase (CK)

Note for serum chemistries: Tests for AST, ALT, ALP, and total bilirubin must be conducted concurrently and assessed concurrently.

Hematology

- White blood cell (WBC) count with differential
- Red blood cell (RBC) count
- Hematocrit
- Hemoglobin

- Platelet count
- Mean corpuscular volume (MCV)
- Mean corpuscular hemoglobin concentration (MCHC)

Urinalysis

- Color
- Glucose

Ketones

Blood

- Appearance
- Specific gravity
- pH
- Bilirubin
- Protein
- Microscopy including WBC/high power field (HPF), RBC/HPF

Pregnancy Test (females of childbearing potential only)

• Urine human chorionic gonadotropin (HCG)

Note: Any female subject who is postmenopausal based on documented results from the serum follicle-stimulating hormone test will not require urine HCG tests in this study. Any female subject who feels that they have had a change in status to postmenopausal at any point during this study can request a serum follicle-stimulating hormone test. If the results show that the subject is postmenopausal, then the subject will not require any further urine HCG tests.

Additional Tests

- Lipid profile (HDL, LDL, cholesterol, triglycerides, direct LDL when triglycerides are > 400 mg/dL) requiring a fasting blood sample of at least 8 hours
- Immunology profile: ANA, extractable nuclear antigen (RNP, Sm, SSA, SSB), quantitative immunoglobulins

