2.4 Sample Size

Sample size estimation is based on the number of subjects who have completed the treatment period of study CD1013. A total of 307 subjects have been randomized in study CD1013. Assuming that 20% of subjects will be lost to follow up or discontinue from study CD1013, there will be a total of approximately 240 subjects who will be eligible for this long-term safety study.

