3.1.1 Analysis windows

Analysis visit windows will be used for all scheduled assessments to map longitudinal observations to scheduled visits and thereby allow for by-visit analyses, since not all assessments are performed on the scheduled day. Unless otherwise specified, all longitudinal efficacy and safety data analyses will be based on the analysis visit windows. The analysis visit windows will be calculated by bisecting the interval between adjacent scheduled visit days and will be specified in the SPP.

The actual assessment day will be mapped to the windows defined for each scheduled study visit with following rules:

- If more than one assessment falls within a visit window, the closest non-missing assessment to the scheduled day will be used in the analysis.
- If two non-missing assessment actual dates are equidistant from the target day, the earlier visit will be used in the analysis.

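### The SAP counts laboratory and vital-sign limit crossings by visit only and specifies no count of subjects who ever cross a limit

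*SAP*

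**What the plan says.** **Tabulation.** SAP 3.8.5 says of laboratory limits (Appendix E): "Number of subjects with TELVC will be summarized by visit". SAP 3.8.6.1 repeats the sentence for vital-sign limits (Appendix F). For shifts, 3.8.5 says: "The shift from baseline in hematology, serum chemistry, lipid profile, and urinalysis parameters will be summarized by visit". The other planned laboratory outputs are descriptive statistics and changes from baseline by visit (3.8.5) and data listings (3.1).

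**Which value counts.** SAP 3.1.1 applies analysis windows to longitudinal safety data unless something else is specified: "If more than one assessment falls within a visit window, the closest non-missing assessment to the scheduled day will be used in the analysis". Section 3.8.6.1 does specify something else for vital signs: by-visit summaries use the first pre-dose reading, "but all measurements will be considered for the TELVC classification". Section 3.8.5 has no matching sentence for laboratory values. Protocol 5.2.5 adds: "Abnormal laboratory results should be repeated as soon as possible (preferably within 24 to 48 hours)".

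**What the adverse event tables catch.** Protocol 6.1.1: "Nonserious AEs will only be captured during the first year of subject's participation in the study". The exceptions are non-serious events that lead to interruption of the product or discontinuation from the study. Serious events and AESIs are captured throughout. SAP 3.8.2 defines the hepatic AESI as raised ALT or AST together with raised bilirubin, and 3.8.4 gives AESIs a subject rate over the whole exposure period.

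**The concern.** The primary objective is long-term safety and tolerability, and Protocol 7.3.1 names chemistry, hematology, urinalysis and vital signs among the variables used to assess it. A reader of the study report will want to know how many subjects ever reached, say, ALT of 3 × ULN or lymphocytes of 0.5 × 10⁹/L or below. A by-visit table does not show whether one subject was abnormal at every visit or a different subject was abnormal at each.

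The adverse event tables do not fill the gap. After year 1, a non-serious laboratory event is captured only if it is an AESI or leads to interruption or discontinuation. Under Protocol 6.1.1, a value judged not medically significant and needing no intervention is not reported as an adverse event in any year. The hepatic AESI needs both components, so isolated ALT or AST elevations fall outside it. Limit crossings outside these categories therefore have no planned subject-level summary over the study.

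**Working it through.** **1. Denominator.** SAP 2.4 starts from this: "A total of 307 subjects have been randomized in study CD1013". With 20% assumed lost, 307 × (1 − 0.20) = 245.6, which agrees with the stated figure of approximately 240. I use 240.

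**2. Number of post-baseline visits**, from Protocol 5.1.2 and 5.1.3 and Tables 5.1-1 and 5.1-2:
- Chemistry and hematology: Weeks 4 and 8 (2) + every 12 weeks from Week 12 to Week 144 (12) + Week 156 (1) + Visits 41 and 43 (2) = 17.
- Vital signs: every 4 weeks from Week 4 to Week 152 (38) + Week 156 (1) + Visits 41 to 43 (3) = 42.

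**3. What a by-visit row allows.** Let *p* be the proportion crossing a limit at each visit and *k* the number of visits. The proportion ever crossing is
- *p*, if the same subjects cross every time (minimum);
- 1 − (1 − *p*)^*k*, if visits are independent;
- min(1, *kp*), if different subjects cross every time (maximum).

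The documents give no TELVC rate, so *p* is an assumption. Full attendance is also assumed.

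| Domain | *p* | Minimum | Independent | Maximum |
|---|---|---|---|---|
| Chemistry/hematology, *k* = 17 | 0.5% | 0.5% (1) | 8.2% (20) | 8.5% (20) |
| | 1% | 1% (2) | 1 − 0.99^17 = 15.7% (38) | 17% (41) |
| | 2% | 2% (5) | 1 − 0.98^17 = 29.1% (70) | 34% (82) |
| Vital signs, *k* = 42 | 1% | 1% (2) | 1 − 0.99^42 = 34.4% (83) | 42% (101) |

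Subjects out of 240 are in brackets, rounded.

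**4. Effect of dropout.** If attendance falls linearly from 240 to 60% (144), mean attendance over the 17 visits is (240 + 144)/2 = 192. The maximum at 1% is then 0.01 × 17 × 192 = 32.6, about 33 subjects or 13.6% of 240. The range narrows, but the ambiguity remains.

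**5. Loss through the window rule.** Suppose an abnormal value is drawn *d* days before the target day and a normal repeat follows *r* days later. The repeat replaces it if |*d* − *r*| < *d*, that is, if 0 < *r* < 2*d*. With *r* = 1 this happens for any draw at least 1 day early. With *r* = 2 it happens for any draw at least 2 days early; at *d* = 1 the two tie, and 3.1.1 takes the earlier. Visits may be up to 7 days early (Protocol 5.1.2), so the case is an ordinary one. An abnormal scheduled value drawn on or after the target day is kept. An unscheduled abnormal value is lost whenever the scheduled draw in its window lies closer to the target.

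**The case against.** The strongest reply is that the gap may be smaller in practice than on paper. SAP section 1 places table templates in a separate statistical programming plan, which was not available, and a by-visit template may carry an any-time row. Listings sorted by subject would let anyone derive the count. Protocol 7.3.1 assesses safety primarily through adverse events and asks only for a descriptive summary of other variables, which by-visit tables satisfy. No decision rule depends on the missing count.

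All of that stands, and it rules out several stronger readings:
- A reader might infer that the count will never be produced. The documents show only that the SAP does not specify it.
- A reader might infer that the by-visit tables are the only record of laboratory safety in years 2 and 3. They are not: serious events, AESIs, events causing interruption or discontinuation, descriptive by-visit statistics and listings all continue, and the hepatic composite has a subject rate over the whole exposure period.
- A reader might expect scattered events to appear as a flat 1%. The 1% is an assumption. If 41 single crossings fall at random over 17 visits, the mean is 41/17 = 2.4 per visit, but simulated visit counts mostly lie between 0 and 6 (0% to 2.5% of 240).
- A reader might take the independence figures as upper limits. They are not; the maximum is *kp*. Persistence within a subject pulls the answer towards the minimum.

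The reply does not remove the main point. A central safety summary belongs in the SAP. A count left to listings has no stated rule on repeats, unscheduled values or denominator, and the rule that is stated for laboratory values can discard abnormal ones.

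**Conclusion.** The concern holds as a gap in specification. The SAP text plans TELVCs and laboratory shifts by visit only, and by-visit counts cannot yield the number of subjects who ever cross an Appendix E or F limit. Read literally, 3.1.1 can also undercount laboratory crossings within a visit, because 3.8.5 lacks the exception that 3.8.6.1 makes for vital signs.

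Under the assumed 1% per visit and full attendance, the unresolved range is 1% to 17% of subjects for a chemistry or hematology limit and 1% to 42% for a vital-sign limit. These figures show how little a by-visit row determines; they do not predict event rates. The adverse event analysis is unaffected. The change is worth making because laboratory and vital-sign data are named parts of the primary assessment.

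**What to change.** In SAP 3.8.5 and 3.8.6.1:

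1. For each Appendix E and F limit, add the number and percentage of subjects with at least one post-baseline TELVC. Use all scheduled, repeat and unscheduled values through the end of study participation. Do not borrow the cut at last dose + 85 days from 3.8.4: Visit 43 has a ±7-day window, so values drawn on days 86 to 92 would be lost.
2. Use as denominator the subjects with at least one post-baseline value and, where the limit involves a change, a baseline value.
3. Add a shift table from baseline to worst post-baseline value for laboratory parameters.
4. State in 3.8.5 that all laboratory values count toward the TELVC classification, not only the one closest to the target day.
5. Keep the by-visit tables as supporting output.

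I would not add a rate per 100 patient-years. Most chemistry draws are 12 weeks apart, so onset is known only to the interval.

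The cost is SAP wording and one or two tables per domain, from data already collected. The drawback is that any-time counts including unscheduled values depend partly on how often a subject is tested; a footnote should say so.
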